9.7 Subject Disposition

Enrollment status for all subjects will be summarized in a table for each investigator site by randomized treatment and overall for all subjects in addition to the number of screen failures and number of randomized subjects.

Summary for subject disposition by treatment and overall for all subjects will include:

- Number of screen failures for all subjects only
- Number of randomized subjects
- Number and percentage of implanted subjects
- Number and percentage of subjects with eyes touched with study IOL
- Number and percentage of subjects for each of the study sets (ITT Set, mITT Set, Modified Safety Set, PP Set, and Best Case Set)
- Number and percentage of subjects who completed the study.
- Number and percentage of subjects discontinued from the study, with subcategories for number and percentage of subjects who discontinued before first implant, discontinued after the first implant but before the second implant, and discontinued after the second implant. In addition, for those subjects that did not complete the entire study, the reason for study discontinuation will be summarized.
- Number and percentage of subjects who completed through Visit 4 and who discontinued prior to Visit 4 and reason for discontinuation prior to Visit 4.

Percentages will be based on number of randomized subjects for subject disposition summary.

A summary for eyes disposition by treatment and overall for all subjects will include:

- Number of randomized eyes
- Number of treated eyes
- Number and percentage of implanted eyes
- Number and percentage of eyes touched with study IOL
- Number and percentage of eyes for each of the study populations (mITT, Modified Safety Set, PP Set, and Best Case Set)

Percentages will be based on number of randomized eyes for eyes disposition summary unless specified otherwise.

Subject accountability by visit up to Visit 5 will be provided for summaries of the following categories by treatment group and overall for all subjects based on the ITT Set, mITT Set, PP Set, and Best Case Set:

- Total number of all subjects
- Total number of subjects with an eye touched with study IOL
- Total number of implanted subjects
- Number of subjects available for analysis by visit
- Number of subjects discontinued by visit
- Number of subjects missing a scheduled visit but seen later by visit
- Number of subjects not seen but accounted for by visit
- Number of subjects lost to follow-up by visit
- Active (represents the number of subjects that have not reached the time associated with a visit.) by visit
- Percent accountability presented by visit. % Accountability is calculated as $100 * (\text{Available for analysis}) / (\text{Enrolled} - \text{Discontinued} - \text{Active})$.

Subject accountability by visit up to Visit 5 for each site will also be summarized similarly based on the ITT Set.

Eye accountability by visit up to Visit 5 will be summarized in the same way as the subject accountability by visit.

Disposition, randomization, enrollment status, inclusion/exclusion criteria, subject accountability by visit, and population listing data for randomized subjects will be presented in data listings.

10 Protocol Deviations

Protocol deviations will be evaluated for all randomized subjects. Major protocol deviations will be determined by a masked evaluation prior to the unmasking of the study treatment. Numbers of subjects with any protocol deviations, any major protocol deviations, any minor protocol deviations, and any COVID-19 related deviations will be summarized by treatment and overall for all subjects for the mITT Set. In addition, major protocol deviations leading to exclude subjects from the PP set will be determined by a masked evaluation prior to the unmasking of the study treatment. Numbers of subjects with major protocol deviations will also be summarized by treatment and overall for all subjects for the mITT Set.

All protocol deviations will be presented in a data listing.

11 Demographic, Pre-Operative, and Operative Variables

Demographics at the subject level will be summarized by treatment group for the mITT Set, Modified Safety Set, PP Set, and Best Case Set. Pre-operative variables and operative variables will be summarized by treatment group for the first eyes, the second eyes, and all eyes separately for the Modified Safety Set.

Demographic data will include gender, age in years at signing of informed consent form (ICF), age group (18 -64 years, 65 – 84 years, and \geq 85 years), race, ethnicity, first eye (OD, OS), and study phase under which the subject enrolled. Subjects who record more than one race will be grouped into the single category denoted as multi-racial.

The pre-operative variables include:

- Potential Visual Acuity (Snellen: Better than 20/32, 20/32 or Worse, Not Done)
- Axial length (mm)
- Anterior chamber depth (mm)
- Targeted refraction (D)
- Corneal topography (Normal, Abnormal)
- Cataract type (nuclear, cortical, posterior sub-capsular, combination)
- Cataract density (slight [1+], moderate [2+], dense [3+], very dense [4+])

The operative variables will include:

- IOL Power (+16.0 to +24.0 by increments of 0.5)
- Femtosecond laser used for surgery (Yes, No) and type if laser used (corneal incision, anterior capsulotomy, cataract fragmentation)
- Was study lens successfully implanted? (Yes, No)

Data listings for demographic data, pre-operative variables, and operative variables will be presented.

12 Concomitant Medications

Medications will be coded using World Health Organization (WHO) Drug Dictionary (Global B2, March 2018). Concomitant medications will be defined as medications used during the operation or after the operation. Ocular and non-ocular concomitant medications used at the subject level will be summarized separately by the therapeutic drug class (Anatomical Therapeutic Chemical [ATC] 4 classification), preferred name, and treatment for the Modified Safety Set. If the ATC 4 classification is not provided, the next lowest classification that is provided in the coding dictionary will be used. The preferred name will be defined as the active ingredient; if the active ingredient is not provided or includes more than two ingredients (e.g., multivitamins) then the drug name will be presented as the preferred name.

Prolonged use of anti-inflammatory medication beyond 6 weeks will also be summarized by drug class, preferred name, and treatment for the Modified Safety Set.

Reported and coded terms (drug class and preferred name) for all medications will be presented in a data listing. Prolonged use of anti-inflammatory medication beyond 6 weeks will be presented in separate listing.

13 Statistical Analyses

13.1 Primary Safety Analyses

13.1.1 First Eyes with at Least One Ocular Treatment-Emergent SAEs

The proportion of first Modified Safety Set eyes with at least one ocular treatment-emergent serious adverse event (TE-SAE) will be summarized using categorical summary statistics by treatment received. Each eye will be counted only once in the calculation of the rate. Similar supportive analyses will be presented for second eyes and all eyes for the Modified Safety Set.

13.1.2 SSIs Related to the Optical Properties of the IOL

The SSIs related to the optical properties of the IOL will be defined as IOL explantation, replacement, or repositioning due to subject intolerance of visual symptoms not adequately improved by spectacle correction. The investigators will apply this definition to classify each SSI as either related to the optical properties of the IOL or not related to the optical properties of the IOL.

Each eye will be classified as either having undergone an SSI related to the optical properties of the IOL or not having undergone such an intervention. Missing data will not be imputed.

First eyes with SSIs related to the optical properties of the IOL will be summarized categorically by actual treatment received for the Modified Safety Set. A two-sided 90% CI around the difference in proportions (Test minus Control) will be constructed using the Newcombe-Wilson score method without continuity correction. If the upper confidence limit (which is equivalent to a one-sided 95% upper confidence limit) is less than 0.034 or if the proportion in both groups is zero, then the null hypothesis will be rejected and it will be concluded that the Test IOL is statistically non-inferior to the Control IOL in this outcome.

As supportive analyses, the rates of SSIs due to the optical properties of the lens in second eyes and in all eyes will be presented using descriptive statistics by treatment group.

All SSIs will be presented in a data listing.

13.1.3 ISO Grid AEs

Cumulative and persistent ISO grid AEs listed in Table 2 will be summarized categorically for the Modified Safety Set by treatment received. The primary statistical analysis will include first Modified Safety Set eyes with the Test IOL.

Table 2. SPE Rate for Posterior Chamber IOL AEs (ISO 11979-7:2018, Table E.2)

Adverse Event	SPE Rate
Cumulative	
Cystoid macular edema	3.0
Hypopyon	0.3
Endophthalmitis ^a	0.1
Lens dislocated from posterior chamber	0.1
Pupillary block	0.1
Retinal detachment	0.3
Secondary surgical intervention ^b	0.8
Persistent	
Corneal stroma oedema	0.3
Cystoid macular oedema	0.5
Iritis	0.3
Raised IOP requiring treatment	0.4

^a Endophthalmitis is defined as intraocular inflammation (sterile or infectious) leading to diagnostic vitreous tap and use of intraocular antibiotics.

^b Excludes posterior capsulotomies.

The numerator for each cumulative AE will be the number of first Test group eyes reporting the AE at least once after surgery. The denominator for cumulative AEs will be the number of first Test group eyes.

The numerator for each persistent AE will be the number of first eyes in the Test group with the event at Post-Operative Visit 5. The denominator for persistent AEs will be the number of first Test group eyes present at Post-Operative Visit 5.

For each ISO grid AE, a one-sided exact binomial test comparing the proportion of Test group eyes with the AE to the relevant control rate will be completed. If the resulting p-value is less than or equal to 0.05, then the null hypothesis will be rejected.

Statistical success with respect to comparing these endpoints to the historical controls will have been achieved if none of the null hypotheses are rejected for the Test IOL treatment group.

As supportive analysis, the incidence of SPE AEs (as defined in ISO 11979-7) in second eyes and all eyes will be presented using descriptive statistics by AE type and by treatment group.

The summary and analysis for first eyes will also be performed by age group (<65 years and ≥ 65 years) and by site.

All ISO Grid AEs will be presented in a data listing.

13.2 Secondary Safety Analyses

13.2.1 Subjects Experiencing at Least One Severe Visual Disturbance

The rates of visual disturbances reported as “severe” for Questions 1B – 10B by subjects, as well as the rates of visual disturbances reported as “very” bothersome for Questions 1C-10C by subjects, using the QoV questionnaire measure through Post-Operative Visit 4 (Day 120 to 180 after second eye IOL implantation) will be summarized using descriptive statistics by treatment for the Modified Safety Set. Each subject will be counted only once in the calculation of the rate.

13.2.2 Contrast Sensitivity

Contrast sensitivity will be evaluated for a subset of subjects. Binocular contrast will be assessed in log units two times per subject at Post-Operative Visit 4 (Day 120 to 180 after second eye IOL implantation) or (in the case of a capsulotomy after Visit 4) Post-Operative Visit 5 (Day 330 to 420 after second eye IOL implantation) under each of the conditions on Table 3.

Table 3. Binocular Contrast Sensitivity Conditions

Lighting Condition	Spatial Frequencies
Photopic lighting with glare	3, 6, 12, and 18 cycles per degree (cpd)
Mesopic lighting with glare	1.5, 3, 6, and 12 cpd
Mesopic lighting without glare	1.5, 3, 6, and 12 cpd

For each subject, the two values will be recorded under each combination of conditions. The values reported in EDC database will be converted for analyses following the rule: values of 1 will be set as missing and all remaining values will be multiplied by -1 to convert log contrast to log contrast sensitivity. The average of converted values will be used for analyses. If a subject has only one converted value for a certain condition, then the single value will be considered the average. Only the converted values will be used for tables, listings, and figures.

Contrast sensitivity (in log units) will be summarized descriptively using continuous summary statistics by lighting condition (photopic or mesopic and with glare or without glare), spatial frequency, treatment received, and visit for the Modified Safety Set. Since each subject will have been assessed once at either Post-Operative Visit 4 (Day 120 to 180 after second eye IOL implantation) or Post-Operative Visit 5 (Day 330 to 420 after second eye IOL implantation), summaries will also be presented by lighting condition, spatial frequency, and treatment received. If the subject was assessed at both Post-Operative Visit 4 (Day 120 to 180 after second eye IOL implantation) and Post-Operative Visit 5 (Day 330 to 420 after second eye IOL implantation), then the value from Post-Operative Visit 4 (Day 120 to 180 after second eye IOL implantation) will be used if no capsulotomy was performed for the subject. Otherwise, the value from Post-Operative Visit 5 (Day 330 to 420 after second eye IOL implantation) will be used.

Estimates of the differences between treatment groups, with two-sided 95% confidence intervals, will be provided by lighting condition and spatial frequency using the values

obtained at either Post-Operative Visit 4 (Day 120 to 180 after second eye IOL implantation) or Post-Operative Visit 5 (Day 330 to 420 after second eye IOL implantation).

Mean log contrast sensitivity will be plotted versus spatial frequency, with the treatment groups overlaid, separately by lighting condition and visit.

The contrast sensitivity data will be presented in a data listing, which will include the value used to compute statistics by lighting condition and spatial frequency.

13.2.3 Adverse Events

All AEs will be coded using the Medical Dictionary for Regulatory Activities (MedDRA) version 22.1. Ocular TEAEs will be defined as ocular AEs with onset dates on or after the date of study lens implantation for the eye. Non-ocular TEAEs are defined as non-ocular AEs with onset dates on or after the date of first study lens implantation. Ocular AEs will be AEs with an Eye designation of OD, OS, or OU in the electronic Case Report Form. Non-ocular AEs will be AEs with an Eye designation of N/A.

Ocular TEAEs in first eyes and second eyes will be summarized separately by treatment received for the Modified Safety Set according to the following list. Summaries of all eyes will be provided separately at the eye and subject levels.

- Overall summary of TEAEs (the number and percentage of subjects [or eyes] who experienced at least one ocular TEAE, ocular TE-SAE, ocular TEAEs by maximum severity, ocular TEAEs by strongest relationship to study device, ocular TEAEs by strongest relationship to surgical procedure, ocular TE-SAEs by strongest relationship to study device, and ocular TE-SAEs by strongest relationship to surgical procedure)
- Ocular TEAEs by system organ class (SOC) and preferred term (PT)
- Ocular TEAEs by SOC and PT and by age group (<65 years and \geq 65 years)
- Ocular TEAEs by SOC and PT and by site
- Ocular TE-SAEs by SOC and PT
- Ocular TEAEs by SOC, PT, and strongest relationship to study device
- Ocular TEAEs by SOC, PT, and strongest relationship to surgical procedure
- Ocular TE-SAEs by SOC, PT, and strongest relationship to study device
- Ocular TE-SAEs by SOC, PT, and strongest relationship to surgical procedure
- Ocular TEAEs by SOC, PT, and maximum severity
- Ocular TE-SAEs by SOC, PT, and maximum severity

Non-ocular TE-SAEs at the subject level will also be summarized.

The incidence of the following further defined Ocular TEAEs of special interest will be summarized categorically by treatment group.

- Endophthalmitis - intraocular inflammation requiring vitreous tap and use of intraocular antibiotics
- Toxic anterior segment syndrome (TASS) - An acute, noninfectious inflammation of the anterior segment of the eye that develops within 24 to 48 hours after surgery and is

characterized by corneal edema and accumulation of white cells in the anterior chamber of the eye

- Mechanical pupillary block - Mechanical pupillary block represents a shallowing of the peripheral and/or central anterior chamber with or without elevation of intraocular pressure (IOP) by obstruction of the flow of aqueous humor from the posterior chamber through the pupil to the anterior chamber. This may be induced by the crystalline lens, vitreous face, or implanted devices
- Chronic anterior uveitis - anterior segment inflammation characterized by grade 1+ cell or greater persistent for greater than 3 months after surgery, or relapses in less than 3 months after discontinuation of therapy, or the subject is maintained on therapy for more than 3 months to control inflammation
- Corneal edema - Corneal swelling (stromal or epithelial) resulting in BCDVA of 20/40 or worse, at ≥ 1 month postoperatively
- Rhegmatogenous retinal detachment (RD) – partial or complete RD associated with retinal tear
- Increased IOP - Elevation of IOP > 10 mmHg above the baseline and to a minimum of 25mmHg
- Clinically significant cystoid macular edema - Macular edema diagnosed by clinical exam and adjunct testing (e.g., OCT, fluorescein angiography or other method) and which results in reduced BCDVA to 20/40 or worse at Visit 3A for the first eye or Visit 3B for the second implanted eye or later

All AEs, Ocular SAEs, ocular AEs related to study device or surgical procedure, AEs of special interest, and non-ocular SAEs will be presented in separate data listings.

13.3 Primary Effectiveness Analyses

All data collected for corrected and uncorrected visual acuity assessments will be presented in data listings, separated by monocular and binocular as well as photopic and mesopic.

13.3.1 Photopic Monocular BCDVA

Photopic monocular BCDVA (logMAR) in first eyes at Post-Operative Visit 4 (Day 120 to 180 after second eye IOL implantation) will be summarized using continuous summary statistics by treatment group. Imputation of missing data is not conservative in non-inferiority testing. Therefore, missing data will not be imputed for the BCDVA non-inferiority test. An analysis of covariance (ANCOVA) model will be constructed with BCDVA as the dependent variable and treatment and site as fixed factors. The treatment effect (least squares [LS] mean for Test group IOL minus LS mean for Control group IOL) will be estimated in addition to a two-sided 90% CI. If the upper confidence limit (equivalent to a one-sided upper 95% confidence limit for the treatment effect) is less than 0.1, then the Test lens will be statistically non-inferior to the control lens. The summary and analysis will be performed for both ITT and mITT Sets.

The previous continuous summary statistics will also be provided for the PP Set. However, non-inferiority will not be evaluated with the PP Set, and statistical success will not depend upon the results of the PP analysis.

The BCDVA at Post-Operative Visit 4 (Day 120 to 180 after second eye IOL implantation) for the Test group will be summarized categorically (20/20 or better, 20/25 or better, 20/32 or better, 20/40 or better, and worse than 20/40) for the ITT, mITT, and Best Case Sets. Two-sided exact binomial 90% CIs around the proportions of eyes 20/40 or better will be presented. Categorical summaries will use whole line binning as shown in Table 4.

Table 4. logMAR to Snellen Conversion Table

logMAR Value	Cumulative Snellen Category
≤ 0.00	20/20 or better
≤ 0.10	20/25 or better
≤ 0.20	20/32 or better
≤ 0.30	20/40 or better
> 0.30	Worse than 20/40

For the analyses of the ITT, mITT, and Best Case Sets, one-sided exact binomial tests comparing the proportion of Multifocal IOL eyes with BCDVA 20/40 or better to the relevant control rate (92.5% for all eyes in ITT and mITT Sets and 96.7% for Best Case Set eyes) will be performed, and p-values will be presented. If the p-value is less than or equal to 0.05, then the null hypothesis will be rejected. Similar analysis will be performed for first eyes and second eyes as supportive analysis.

If the null hypothesis is not rejected for the ITT, mITT, and Best Case Sets in the primary analyses, then it will be concluded that the Multifocal IOL is statistically successful in this outcome.

BCDVA will also be summarized by treatment group for the mITT Set at Post-Operative Visit 4 (Day 120 to 180 after second eye IOL implantation), both continuously and categorically, with both mutually exclusive and cumulative categories from 20/20 or better through worse than 20/40, stratified by the following variables.

- Age group (< 65 and ≥ 65 years)
- Adverse events in the ISO Grid
- Site

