### **8.1 Subject Inclusion Criteria**

This study will include subjects who meet all of the following inclusion criteria:

1. Subjects must be 22 years of age or older on the date the Informed Consent Form (ICF) is signed.
2. Subjects must have the capability to understand and provide written informed consent on the Institutional Review Board (IRB)/Independent Ethics Committee (IEC) approved Informed Consent Form (ICF) and authorization as appropriate for local privacy regulations.
3. Subjects must have a BCDVA equal to or worse than 20/40 in each eye, with or without a glare source, due to a clinically significant cataract (cortical, nuclear, subcapsular, or combination) that is considered amenable to treatment with standard phacoemulsification cataract extraction and capsular IOL implantation.
4. Subjects must have a BCDVA projected to be better than 20/32 after IOL implantation in each eye, as determined by the medical judgment of the Investigator or measured by potential acuity meter (PAM) testing, if necessary.

5. Subjects must have clear intraocular media other than the cataract in both eyes.
6. Contact lens wearers must demonstrate a stable refraction (within  $\pm 0.50$  D for both sphere and cylinder) in both eyes, as determined by manifest refraction on two consecutive examination dates after discontinuation of contact lens wear.
7. Subjects must require an IOL power from +16.0 diopter (D) to +24.0 D in both eyes.
8. Subjects must be willing and able to comply with all treatment and follow-up study visits and procedures, and to undergo second eye surgery within 7-30 days of the first eye surgery.

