## **13.5.3 Primary Effectiveness Analyses**

### **13.5.3.1 Photopic Monocular BCDVA**

Photopic monocular BCDVA in first eyes will be assessed at Post-Operative Visit 4 using the methods described in [Appendix B](#) on Methods of Clinical Evaluation. The total number of letters correct will be entered into the electronic case report form.

The number of letters correct will be converted to logMAR units using the following equation:

$$\text{logMAR BCDVA} = 1.7 - 0.02 \times \text{letters correct}$$

Photopic monocular logMAR BCDVA in first implanted eyes at Post-Operative Visit 4 will be summarized using continuous summary statistics by treatment group for the mITT Set. Imputation of missing data is not conservative in non-inferiority testing. Therefore, missing data will not be imputed for the BCDVA non-inferiority test. A statistical model will be constructed with BCDVA as the dependent variable and treatment and site as fixed factors. The treatment effect (least squares mean Test group IOL VA minus least squares mean Control group IOL VA) in logMAR units will be estimated in addition to a two-sided 90% confidence interval. If the upper confidence limit (equivalent to a one-sided upper 95% confidence limit for the treatment effect) is less than 0.1, then the Test lens will be statistically non-inferior to the control lens.

The previous continuous summary statistics will also be provided for the Per Protocol Set. However, non-inferiority will not be evaluated with the PP Set and statistical success will not depend upon the results of the PP analysis.

BCDVA at Visit 4 for the Test group will be summarized categorically (20/20 or better, 20/25 or better, 20/32 or better, 20/40 or better, and worse than 20/40) for the mITT and Best Case Sets. Two-sided exact binomial 90% confidence intervals around the proportions of eyes 20/40

or better will be presented. Categorical summaries will use whole line binning as shown in the following logMAR to Snellen conversion table ([Table 3](#)):

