### **13.6.6 Management of Potential Confounding Factors**

Randomization will be stratified by site. Site will be included in the statistical models for the analyses of continuous primary endpoints.

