## 17 Appendices

### Appendix A STUDY FLOW CHART

Examination	Pre-Op 0A/B (Both Eyes)	Operative 00A (1 st Eye)	Post-Op 1A (1 st Eye)	Post-Op 2A a (1 st Eye)	Post-Op 3A (1 st Eye)	Operative 00B (2 nd Eye)	Post-Op 1B (2 nd Eye)	Post-Op 2B (2 nd Eye)	Post-Op 3B (2 nd Eye)	Post-Op 4 (Both Eyes)	Post-Op 5 (Both Eyes)	For sub- study only: Post-Op 6 (Both eyes)
	Day -30 to -5	Day 0	Day 1 to 2	Day 7 to 14	Day 30 to 60	Day 7 to 30	Day 1 to 2 Post Visit 00B	Day 7 to 14 Post Visit 00B	Day 30 to 60 Post Visit 00B	Day 120 to 180 Post Visit 00B	Day 330 to 420 Post Visit 00B	Day 2- 30 post Visit 5
Informed Consent	X											X o
Demographics	X											
Ocular and Non-Ocular Medical History	X											
Inclusion/Exclusion	X	X b				X b						X p
Subject Questionnaires c	X									X		
Potential Visual Acuity	X											
Corneal Topography	X											
Targeted Refraction / IOL Power Calculation / Axial Length Determination/Anterior Chamber Depth	X											
Chord length $\mu$	X									X	X	
Keratometry	X				X				X	X	X	

Examination	Pre-Op 0A/B (Both Eyes)	Operative 00A (1 st Eye)	Post-Op 1A (1 st Eye)	Post-Op 2A a (1 st Eye)	Post-Op 3A (1 st Eye)	Operative 00B (2 nd Eye)	Post-Op 1B (2 nd Eye)	Post-Op 2B (2 nd Eye)	Post-Op 3B (2 nd Eye)	Post-Op 4 (Both Eyes)	Post-Op 5 (Both Eyes)	Post-Op 6 (Both eyes)
	Day -30 to -5	Day 0	Day 1 to 2	Day 7 to 14	Day 30 to 60	Day 7 to 30	Day 1 to 2 Post Visit 00B	Day 7 to 14 Post Visit 00B	Day 30 to 60 Post Visit 00B	Day 120 to 180 Post Visit 00B	Day 330 to 420 Post Visit 00B	Day 2- 30 post Visit 5
Manifest Refraction (ETDRS)	X			X	X			X d	X d	X	X	
Randomization		X										
Operative Procedures		X				X						
Photopic Pupil Size	X								X d	X		
Mesopic Pupil Size	X									X		
UCDVA – photopic, monocular (ETDRS)	X		X	X	X		X	X	X	X	X	
UCDVA- photopic, binocular (ETDRS)								X	X	X	X	
BCDVA – photopic, monocular (ETDRS)	X			X	X			X	X	X	X	
BCDVA – photopic, binocular (ETDRS)								X	X	X	X	
UCNVA e,f – photopic, monocular					X				X	X	X	
UCNVA e,f – photopic, binocular									X	X	X	
DCNVA e – photopic, monocular					X g				X f	X f	X f	

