#### 1.1 Preoperative Manifest Subjective Refraction

If the subject has a current pair of glasses for distance vision, they can be measured with a lensometer and these measurements used as the beginning approximate refraction. If the subject does not have glasses for distance vision, retinoscopy or autorefraction may be performed by an examiner proficient in this procedure as the beginning approximate refraction. If the subject is a contact lens wearer, they should be advised to arrive for the preoperative testing wearing spectacles and not their contact lenses.

**AUTOREFRACTION ALONE IS NOT ALLOWED AT ANY POINT IN THIS STUDY.  
RESULTS MUST BE REFINED USING SUBJECTIVE TECHNIQUES.**

The manifest subjective refraction at 4 meters MUST be transferred to the trial frame for BCDVA testing. If for any reason (e.g., dense cataract) manifest refraction cannot be obtained, the results should be documented as not done (ND) and not entered as zeros. In the event of

this occurrence, BCDVA will not be tested and the reason for ND will be required in the source document and eCRF.

Contact lens wearers must demonstrate a stable refraction (within  $\pm 0.50$  D for both sphere and cylinder) on two consecutive exam dates. Stability of the refraction is determined under the following conditions:

- Lenses are not worn for at least 1 week (rigid contact lenses) or 3 days (soft contact lenses) prior to the first refraction used to establish stability and through the day of surgery;
- The two refractions are performed at least 7 days apart.

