Subjects who meet eligibility criteria will be randomly assigned to Group 1 or Group 2 in a 2:1 ratio on the first operative day, Day 0. The first eye implanted will be designated eye A, and the second eye implanted will be designated eye B. The eye with the worse best-corrected distance visual acuity (BCDVA) at the Preoperative Visit will be treated first (eye A) and used in the primary monocular evaluations. If the qualifying visual acuity is obtained with a glare source, the eye with the worse BCDVA with glare will be treated first. If BCDVA is the same for both eyes, the right eye will be treated first. Postoperatively, all eyes will undergo ophthalmic examinations at regular intervals per the study visit schedule through Post-Operative Visit 5 (330 – 420 days after second eye implantation).

[figure not shown]
Study enrollment will occur in three Phases as follows:

- Phase I/Pilot – Approximately 27 Group 1 (Test IOL) subjects will be enrolled and followed to Post-Operative Visit 3B (30 to 60 days after second eye IOL implantation) before a decision is made to initiate Phase II enrollment. Approximately 14 subjects will also be randomized to Group 2 (Control IOL) during this phase. A designated unmasked statistician(s) will summarize Phase I/Pilot distance-corrected near visual acuity (DCNVA) and distance-corrected intermediate visual acuity (DCIVA) data from Group 1 first eyes for review by a clinical team not associated with the study, and the best near and intermediate distances will be selected for Phase II and Phase III evaluation. Phase I safety data will also be summarized for review by an unmasked clinical reviewer not associated with the study, and a decision to initiate

Phase II will be made by the Food and Drug Administration (FDA) based on Phase I data.

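### The BCDVA non-inferiority model is labelled ANCOVA but has no covariate, although pre-operative first-eye BCDVA is collected and could be added at little cost

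*SAP*

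**What the plan says.** For the first primary effectiveness endpoint, SAP 13.3.1 specifies: "An analysis of covariance (ANCOVA) model will be constructed with BCDVA as the dependent variable and treatment and site as fixed factors". The upper limit of the two-sided 90% interval from this model is compared with 0.10 logMAR. Protocol 13.5.3.1 lists the same two terms without the ANCOVA name: "A statistical model will be constructed with BCDVA as the dependent variable and treatment and site as fixed factors". Protocol 13.6.6 notes that randomisation is stratified by site and adds: "Site will be included in the statistical models for the analyses of continuous primary endpoints". Neither document mentions a baseline covariate.

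The ANCOVA label, again with treatment and site only, is used for monocular DCNVA (SAP 13.3.2), binocular DCNVA (13.4.1) and binocular DCIVA (13.4.3). Other endpoints take it over by reference to 13.3.2. The table of changes in SAP section 16 does not mention it.

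The Appendix A flow chart schedules monocular photopic BCDVA at the Preoperative Visit, when both eyes are examined. SAP 9.6 converts BCDVA to logMAR. SAP 13.5.2 already uses the pre-operative value, to count eyes that lose 0.2 logMAR or more by Visit 4.

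**The concern.** The label and the listed terms do not match. An analysis of covariance has a continuous covariate; this model has none. From the SAP alone, a programmer cannot tell whether the name is loose or a term is missing. The model yields the confidence limit on which a primary endpoint is judged, so the ambiguity should be settled before unmasking.

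The natural covariate is the same measurement, in the same eye, taken before randomisation. Pre-specified adjustment for it would protect the treatment estimate against a chance difference in starting acuity. It would also narrow the interval to the extent that pre-operative acuity predicts acuity at Visit 4. At stake is a little precision and a clear specification, not the validity of the test.

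**Working it through.** **Inputs.** From SAP 6.4: 300 Test and 150 Control eyes, common SD 0.15 logMAR, true difference 0, one-sided alpha 0.05, stated power 99%. From SAP 3.3.5: margin 0.10. From SAP 9.6: one letter is 0.02 logMAR. From Protocol 7.2: up to 25 sites. The correlation r between pre-operative and Visit 4 BCDVA is in neither document. I assume 0 to 0.4 and show the range.

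**Reproducing the stated power.**
- SE = 0.15 × √(1/300 + 1/150) = 0.15 × 0.1 = 0.0150.
- Margin/SE = 0.10/0.0150 = 6.67.
- Power from the noncentral t with 448 df is 0.9999997. With 424 df (450 minus 26 parameters for 25 sites and treatment) it is the same to six decimals. The stated 99% is met with a wide reserve.

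**Effect of the covariate.** The residual SD becomes 0.15 × √(1 − r²), and the SE shrinks by the same factor. The half-width is t(0.95) × SE, and the largest observed difference that still passes is 0.10 minus the half-width.

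| Assumed r | SE | SE reduction | 90% half-width | Largest passing difference | Power if true difference is 0.05 |
|---|---|---|---|---|---|
| 0 | 0.01500 | 0% | 0.0247 | 0.0753 | 0.9539 |
| 0.2 | 0.01470 | 2.0% | 0.0242 | 0.0758 | 0.9601 |
| 0.3 | 0.01431 | 4.6% | 0.0236 | 0.0764 | 0.9674 |
| 0.4 | 0.01375 | 8.3% | 0.0227 | 0.0773 | 0.9765 |

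At the planned true difference of 0, power is above 99.999% in every row. The last column is a what-if; the plan does not assume a difference of 0.05.

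**In letters.** The half-width falls by 0.0005, 0.0011 or 0.0020 logMAR for r of 0.2, 0.3 or 0.4. Divided by 0.02, that is about 0.03, 0.06 or 0.10 of a letter, against a margin of 0.10/0.02 = 5 letters.

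**Near r = 0.** Estimating the slope costs about one residual degree of freedom. The cost and the gain balance when r² is about 1/424, so r is about 0.05. Below that there is no gain, though the loss is negligible.

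**A larger SD.** With SD 0.25, power is 0.9906 unadjusted and 0.9945 at r = 0.3. With SD 0.30 the figures are 0.9539 and 0.9674.

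**The case against.** The strongest reply is that this cannot change the trial's answer. Power is already far above target, the gain is at most about a tenth of a letter over the range assumed, and the plan has a stated reason for its model, since site is the stratification factor. All of that stands.

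The correlation may also be weak. Before surgery, acuity is reduced by the cataract that surgery removes: "Subjects must have a BCDVA equal to or worse than 20/40 in each eye, with or without a glare source". After surgery, its range is narrowed by another entry criterion: "Subjects must have a BCDVA projected to be better than 20/32 after IOL implantation in each eye". This is a fair reason to expect the lower rows of r, and possibly no gain.

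Three practical objections also hold, and they shape the fix:
- The covariate can be absent. If manifest refraction fails, Appendix B section 1.1 says "BCDVA will not be tested and the reason for ND will be required". The documents do not say how often this will happen.
- SAP 9.6 assigns 2.00 to count fingers and 2.30 to hand motion. Such values would have high leverage in a linear term.
- Pre-operative BCDVA does not always decide which eye is eye A. When the qualifying acuity was obtained with glare, acuity with glare decides (SAP 4.1). The covariate must therefore be defined explicitly.

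Adjustment is also not guaranteed to narrow the interval. Apart from the case of r near zero, with 2:1 allocation a common-slope covariate need not reduce the variance if the slope differs between lenses.

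None of this justifies keeping an ANCOVA label on a model without a covariate, or is a strong reason to leave a baseline already in the database unused.

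**Conclusion.** The point holds as a minor one. As written, the BCDVA model is a two-factor ANOVA under the wrong name, and a relevant pre-randomisation measurement is collected but not used in it. The benefit of using it is protection against chance imbalance and a half-width that falls from 0.0247 to between 0.0242 and 0.0227 logMAR if r lies between 0.2 and 0.4. That range is an assumption, not a figure from the plan.

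A reader might go further and infer that the non-inferiority comparison is biased, that its error rate is inflated, or that the test lacks power. The documents do not support this: omitting a baseline covariate from a randomised comparison does none of the first two, and power at the planned inputs is above 99.999% either way. A reader might also infer that a covariate was intended and dropped by mistake. The protocol lists the same two terms and claims no baseline adjustment, so the texts show only a wrong label.

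**What to change.** Before unmasking:
- In SAP 13.3.1, add pre-operative first-eye monocular photopic BCDVA without glare (logMAR) as a continuous covariate beside treatment and site.
- Keep every subject in the model. Where the pre-operative value was not done, insert the overall mean and add a missing-value indicator.
- State how the count-fingers and hand-motion codes (2.00 and 2.30) enter the covariate.
- List the change in SAP section 16, because Protocol 13.5.3.1 names only treatment and site.
- Relabel as ANOVA (treatment, site) any model left without a covariate. This concerns SAP 13.3.2, 13.4.1 and 13.4.3 and the endpoints that refer to 13.3.2. The flow chart has no pre-operative near or intermediate acuity, so relabelling is enough there.

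The cost is one extra model term, one entry in the table of changes, and a rule for missing or extreme baseline values whose frequency is unknown. No new data are needed. Sample size, margin and success rule stay unchanged.
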